4.2. Secondary endpoints

- Persistence of antibodies before the first dose of *Infanrix hexa*.
 - Anti-diphtheria and anti-tetanus seroprotection status, anti-PT, anti-FHA, anti-PRN seropositivity status and antibody concentrations.
- Immunogenicity with respect to components of *Infanrix hexa* and Prevenar 13.
 - Anti-diphtheria, anti-tetanus, anti-poliovirus type 1, anti-poliovirus type 2, anti-poliovirus type 3, anti-HBs, anti-PRP, anti-PT, anti-FHA, anti-PRN and anti-pneumococcal serotypes (1, 3, 4, 5, 6A, 6B, 7F, 9V, 14, 18C, 19A, 19F, 23F) antibody concentrations or titres, one month after the last dose of primary vaccination.
- Immunogenicity with respect to components of *Infanrix hexa*.
 - Anti-PT, anti-FHA, anti-PRN antibody seropositivity status, one month after the last dose of primary vaccination.

- Solicited local and general symptoms.
 - Occurrence of solicited local/general symptoms during the 4-day (Day 0-Day 3) follow-up period after each vaccination.
- Unsolicited adverse events.
 - Occurrence of unsolicited symptoms during the 31-day (Day 0-Day 30) follow-up period after each vaccination.
- Serious adverse events.
 - Occurrence of SAEs from first vaccination dose to study end.

5. ANALYSIS SETS

5.1. Definition

5.1.1. All enrolled subjects

- All subjects for whom study invasive procedure has been achieved and informed consent has been obtained.

5.1.2. Total vaccinated cohort (TVC)

The TVC will include all vaccinated subjects for whom data are available.

- A safety analysis based on the TVC will include all subjects with at least one vaccine administration documented.
- An immunogenicity analysis based on the TVC will include vaccinated subjects for whom data concerning immunogenicity endpoint measures are available.

5.1.3. ATP cohort for analysis of safety

The ATP cohort for analysis of safety will include all subjects from the TVC who complied with the vaccine administration:

- who have received at least one dose of study vaccines according to their random assignment.
- for whom administration route and site of study vaccines is known and according to the protocol.
- who have not received a vaccine not specified or forbidden in the protocol.

5.1.4. ATP cohort for analysis of immunogenicity

The ATP cohort for immunogenicity will include all evaluable subjects from the ATP cohort for safety:

- who meet all eligibility criteria;
- who comply with the procedures and intervals defined in the protocol.
- who do not meet any of the criteria for elimination from an ATP analysis (refer to Section 6.7.2 of the protocol) during the study;
- who do not receive a product leading to exclusion from an ATP analysis as listed in Section 6.7.2 of the protocol;
- who do not present with a medical condition leading to exclusion from an ATP analysis as listed in Section 6.8 of the protocol;
- who are born full term (full term is defined ≥ 37 weeks of gestation);
- for whom data concerning immunogenicity endpoint measures are available. This will include subjects for whom assay results are available for antibodies against at least one study vaccines antigen component.

The interval between the last vaccination visit and post-primary blood sampling, considered for inclusion of a subject will be 21–48 days.

5.2. Criteria for eliminating data from Analysis Sets

Elimination codes are used to identify subjects to be eliminated from analysis. Detail is provided below for each sets.

5.2.1. Elimination from Total vaccinated cohort (TVC)

Code 1030 (Study vaccine not administered at all) and code 900 (invalid informed consent or fraud data) will be used for identifying subjects eliminated from TVC.

5.2.2. Elimination from ATP cohort for safety

5.2.2.1. Excluded subjects

All eliminations from the primary study 116945 [DTPA(BOOSTRIX)-047] will be applicable for this follow up study except for the visit specific elimination codes (2090, 2100 and 2120) in other words the code 1050, 1060, 1070 assigned to the mother in study 116945 [DTPA(BOOSTRIX)-047] will be inherited to the infant.

A subject will be excluded from the ATP cohort for safety and immunogenicity under the following conditions

Code	Decode => Condition under which the code is used
900	Questionable subject => Invalid informed consent or fraudulent data. In case informed consent is obtained retrospectively the subject is not eliminated.
1030	Study vaccine dose not administered at all but subject number allocated => subjects enrolled but not vaccinated
1040	Administration of vaccine(s) forbidden in the protocol Concurrently participating in another clinical study, at any time during the study period, in which the subject has been or will be exposed to an investigational or a non-investigational vaccine/product (pharmaceutical product or device). A vaccine not foreseen by the study protocol administered during the period starting from 30 days before each dose of vaccine and ending 30 days after*, with the exception of inactivated influenza vaccine and other vaccines given as a part of the national/regional immunisation schedule, that are allowed at any time during the study period. *In case an emergency mass vaccination for an unforeseen public health threat (e.g.: a pandemic) is organised by the public health authorities, outside the routine immunisation program, the time period described above can be reduced if necessary for that vaccine provided it is licensed and used according to its SPC or package insert (PI) and according to the local governmental recommendations and provided a written approval of the Sponsor is obtained.
1050	Randomisation failure (subject who received a vaccine not compatible with randomization) This code is inherited from the mother.
1060	Randomisation code broken at the investigator site OR at GSK Safety department. This code is inherited from the mother.
1070	Incomplete vaccination course before treatment withdrawal: =>for instance only part of the multiple planned administrations at one visit has been administered. For instance, Prevenar not administered while Infanrix hexa is. when no study vaccination at a visit, no other study vaccination can occur up to conclusion/drop-out (Ex. No vaccination at visit 2, but vaccinations at visits 1 and 3 would lead to assignment of code 1070). Note that the code would not be proposed for a subject who had vaccination as planned but missed the last vaccination(s) due to drop-out. In the example given previously, the code would not be proposed if the subject had missed also the vaccination at visit 3). This code is also inherited from the mother Site or route of study vaccine administration wrong or unknown.
1080	Vaccine temperature deviation (vaccine administration not as per protocol) => Infanrix hexa vaccine administered despite a Good Manufacturing Practices (GMP) no-go temperature deviation
1090	Expired vaccine administered (vaccine administration not as per protocol)=> Subjects who received an expired Infanrix hexa

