6.3. Immunogenicity

6.3.1. Analysis of immunogenicity planned in the protocol

The primary analysis will be based on the ATP cohort for analysis of immunogenicity. If in any vaccine group, the percentage of enrolled subjects excluded from this ATP cohort is more than 5%, a second analysis based on the TVC will be performed to complement the ATP analysis. All analyses will be descriptive. For each group, at each timepoint that a blood sample result is available:

- Seropositivity rates against PT, FHA and PRN antigens and pneumococcal antigens (1, 3, 4, 5, 6A, 6B, 7F, 9V, 14, 18C, 19A, 19F, 23F) with exact 95% CI [Clopper, 1934] will be calculated.
- Seroprotection rates against diphtheria toxoid, tetanus toxoid, HBs, PRP antigen and poliovirus types 1, 2, 3 antigens (with exact 95% CI [Clopper, 1934]) will be calculated.
- Percentage of subjects with anti-pneumococcal serotypes (1, 3, 4, 5, 6A, 6B, 7F, 9V, 14, 18C, 19A, 19F, 23F) antibody concentrations, depending on the GSK laboratory or WHO reference laboratory assay cut-offs, will be calculated along with its exact 95% CI [Clopper, 1934].
- Percentage of subjects with anti-D and anti-T antibody concentrations ≥ 1.0 IU/mL will be calculated along with its exact 95% CI [Clopper, 1934].
- Percentage of subjects with anti-PRP antibody concentrations ≥ 1.0 $\mu\text{g/mL}$ and anti-HBs antibody concentrations ≥ 100 mIU/mL will be calculated along with its exact 95% CI [Clopper, 1934].
- GMC/GMT with 95% CI will be tabulated for antibodies against each antigen.

For serology results one month after last vaccination dose:

- The vaccine response rates to PT, FHA and PRN (with exact 95% CI) will be calculated.
- The distribution of antibody concentrations/titres for each antigen will be displayed using reverse cumulative distribution curves (RCCs).
- The distribution of antibody concentrations or titres of each antigen will be tabulated.

Additional summaries will be provided based on country.

Handling of missing data:

For a given subject and a given immunogenicity measurement, missing or non-evaluable measurements will not be replaced. Therefore, an analysis will exclude subjects with missing or non-evaluable measurements.

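### Codes 1080 and 1090 screen Infanrix hexa only, so an expired or temperature-failed Prevenar 13 dose does not remove an infant from the according-to-protocol pneumococcal results

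*SAP*

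**What the plan says.** - Protocol Table 13 (section 6.1) lists two study vaccines, Infanrix hexa and Prevenar 13.
- SAP 5.1.3 states: "The ATP cohort for analysis of safety will include all subjects from the TVC who complied with the vaccine administration". Its criteria refer to study vaccines in the plural. SAP 5.1.4 draws the ATP immunogenicity cohort from this set.
- SAP 5.2 makes elimination codes the means of identifying who is removed. The list in 5.2.2.1 opens: "A subject will be excluded from the ATP cohort for safety and immunogenicity under the following conditions".
- Code 1080 applies when Infanrix hexa was the "vaccine administered despite a Good Manufacturing Practices (GMP) no-go temperature deviation".
- Code 1090 reads "Expired vaccine administered (vaccine administration not as per protocol)=> Subjects who received an expired", and the product named next is Infanrix hexa.
- Code 1070 covers the case where "only part of the multiple planned administrations at one visit has been administered. For instance, Prevenar not administered while" Infanrix hexa is. It also covers a wrong or unknown site or route of study vaccine, with no product named. It has a stated limit: "the code would not be proposed for a subject who had vaccination as planned but missed the last vaccination(s) due to drop-out".
- SAP 6.3.1 uses one ATP immunogenicity cohort for all antigens: "GMC/GMT with 95% CI will be tabulated for antibodies against each antigen". Seropositivity rates for the 13 pneumococcal serotypes come from that cohort, and SAP 6.3.2 adds the ≥0.35 µg/mL rates.

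**The concern.** The code list is not consistent about whether the validity of a Prevenar 13 dose matters for per-protocol status. Omitting the injection matters, and so does giving it at the wrong site or by the wrong route. Giving an expired dose, or one that failed its temperature check, does not. These last two faults bear directly on whether the pneumococcal response reflects a valid course.

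At stake are the 13 pneumococcal secondary endpoints. The protocol's rationale includes asking whether maternal antibodies interfere with the response to the co-administered pneumococcal vaccine. A cohort labelled ATP that still holds invalid Prevenar 13 doses describes something other than its label. A reader of Template 5, whose rows for temperature deviation and expiry name no product, would assume that both vaccines had been screened.

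**Working it through.** **Step 1. Does another code catch the fault?** The remaining codes in SAP 5.2.2.1 and 5.2.3.1 cover consent or fraud (900), no vaccine given (1030), forbidden vaccines or another study (1040), randomisation matters inherited from the mother (1050, 1060), eligibility (2010), forbidden medication (2040), medical condition (2050), vaccination dates (2080), sampling dates (2090), missing serology (2100) and incoherent serology or data error (2120). None is conditioned on an expired or temperature-failed dose.

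**Step 2. Outcome by event under the codes as written**

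| Event | Code | ATP pneumococcal results | ATP Infanrix hexa results | Total vaccinated cohort |
|---|---|---|---|---|
| Planned Prevenar 13 dose omitted, Infanrix hexa given | 1070 | out | out | in |
| Infanrix hexa expired or no-go temperature | 1090 / 1080 | out | out | in |
| Prevenar 13 expired or no-go temperature | none | **in** | in | in |

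The last column follows from SAP 5.2.1, where only codes 1030 and 900 remove an infant from the total vaccinated cohort. An infant in the third row is in both cohorts, so comparing the ATP analysis with the complementary one cannot isolate the effect.

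**Step 3. Size per infant.** Protocol section 10.3 expects 10%–30% attrition from 340 per group: 340 × 0.7 = 238 and 340 × 0.8 = 272, as in Table 22; 340 × 0.9 = 306, where the table uses 300. If *a* of *n* validly vaccinated infants exceed a threshold and one more infant below it is kept, the rate falls from *a/n* to *a/(n+1)*. The fall is *(a/n)/(n+1)*, at most *1/(n+1)*:

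- n = 300: 1/301 = 0.33 percentage points
- n = 238: 1/239 = 0.42 percentage points

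**Step 4. Several infants, worst case.** Assumptions not in the documents: about 95% of validly vaccinated infants exceed the threshold, and all *k* retained infants fall below it. The rate is then *a/(n+k)*.

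| n (a) | k = 0 | k = 1 | k = 3 | k = 6 | k = 15 |
|---|---|---|---|---|---|
| 238 (226) | 95.0% | 94.6% | 93.8% | 92.6% | 89.3% |
| 272 (258) | 94.9% | 94.5% | 93.8% | 92.8% | 89.9% |
| 300 (285) | 95.0% | 94.7% | 94.1% | 93.1% | 90.5% |

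For scale, the exact 95% interval at 95% is 91.4–97.4 for n = 238 (half-width 3.0) and 91.9–97.2 for n = 300 (half-width about 2.6), matching Table 22. Even six infants in one group, all non-responders, shift the rate by less than that half-width: 226/238 − 226/244 = 94.96 − 92.62 = 2.34 points. The effect on a GMC cannot be bounded, because the documents give no expected pneumococcal GMC or log-scale standard deviation.

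**The case against.** The best defence is that the plan reaches these infants by other routes. SAP 5.1.4 has a general requirement to follow protocol procedures and visit intervals. Protocol 6.2 keeps temperature-affected investigational products out of use unless the sponsor approves. The headings of codes 1080 and 1090, and all the relevant Template 5 labels, name no product; the Template 5 label for code 1070 is broad enough to cover any dose not given per protocol. This leaves some ambiguity but does not close the gap. The codes put the general criterion into operation, and 1080 and 1090 carry an explicit product restriction. Template 5 gives temperature deviation and expiry their own rows, so 1070 is not their evident place. Protocol 6.2 speaks of investigational products, while section 1.3.1 puts Infanrix hexa under an investigational heading and Prevenar 13 under a separate one, so the reach of the storage rule to Prevenar 13 is itself unclear.

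It is also fair that the pneumococcal endpoints are secondary and every analysis is descriptive. No test or decision depends on them. That limits the consequence; it does not make the wording right.

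A reader might infer more than the documents support:

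- *That Prevenar 13 faults damage the Infanrix hexa results and spare the pneumococcal ones.* They do not. An omitted dose removes the infant from both sets of ATP results; an expired or temperature-failed dose removes the infant from neither.
- *That an omitted Prevenar 13 dose costs every Infanrix hexa endpoint.* The infant stays in the total vaccinated cohort, which is primary for safety and complementary for immunogenicity when more than 5% of a group is excluded.
- *That code 1070 is wrong to remove such infants from the primary endpoint.* Co-administration is the planned regimen and Prevenar 13 uses a diphtheria CRM197 carrier. Protocol Table 23 also gives separate 2, 3, 4 month reference values without and with co-administered Prevenar: FHA 97.8 and 94.8, PRN 97.8 and 95.0, PRP 95.7 and 93.6. The documents report no test of these differences, but they show that co-administration cannot be dismissed as irrelevant. Code 1070 also refers to planned administrations, so a dose never scheduled in a country is not an omission.

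**Conclusion.** The point holds as a wording gap with a small expected effect. By the stated codes, expired or temperature-failed Prevenar 13 doses stay in the ATP pneumococcal results, while an omitted planned dose does not.

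Each affected infant moves a rate by at most about 0.3–0.4 percentage points at 238–300 evaluable infants per group. How many infants are affected is unknown: the documents give no counts, and the Template 5 figures are mock entries copied from other studies. A reader might suppose that excursions cluster by site and so affect several infants together. Nothing in the documents supports or excludes that, so the larger values of *k* above are illustrations only. The documents also give no reason to expect such faults to differ between the two maternal groups.

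The case for acting is that the inconsistency is plain in the text and almost free to remove, not that a material bias has been shown.

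**What to change.** Extend the conditions of codes 1080 and 1090 in SAP 5.2.2.1 to Prevenar 13, at least for the 13 pneumococcal analyses. If the extension is limited to those analyses, add one antigen-specific flag and footnote the pneumococcal tables. Then make the code text and the Template 5 row labels agree on which products they cover.

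Leave code 1070 as it is. Excluding a partly administered co-administration regimen is a defensible per-protocol choice. Making it product-specific would bring infants without the planned co-administration into the primary analysis.

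The cost is a few lines of SAP text, one flag, and a slightly smaller pneumococcal N that may differ from the Infanrix hexa N. The precision lost is negligible: at an observed rate near 95%, removing six infants from 238 widens the exact interval's half-width from 3.00 to 3.08 points.

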5.2.3. Elimination from ATP cohort for immunogenicity

5.2.3.1. Excluded subjects

All eliminations from the primary study 116945 [DTPA(BOOSTRIX)-047] will be applicable for this follow up study except for the visit specific elimination codes (2090, 2100 and 2120).

A subject will be excluded from the ATP cohort for immunogenicity when he/she is excluded from the ATP cohort for safety (see Section 5.1.3)

The following additional codes will be used:

Code	Decode => Condition under which the code is used
2010	
Protocol violation (inclusion/exclusion criteria) including age and excluding codes mentioned below.
 
A male or female between, 6 and 14 weeks of age (including 6 weeks and up to and including 14 weeks and 6 days of age) at the time of the first vaccination.
 
Healthy subjects as established by medical history and clinical examination before entering into the study.
 
This code is also inherited from the mother

2040	
Administration of any medication forbidden by the protocol=>
 
Immunosuppressants or other immune-modifying drugs administered chronically (i.e. more than 14 days) since birth. For corticosteroids, this will mean prednisone \geq 0.5 mg/kg/day, or equivalent. Inhaled and topical steroids are allowed.
 
Long-acting immune-modifying drugs administered at any time during the study period (e.g. infliximab).
 
This code is also inherited from the mother

2050	
Underlying medical condition forbidden by the protocol =>
 
Subjects may be eliminated from the ATP cohort for immunogenicity if, during the study, they incur a condition that has the capability of altering their immune response (e.g. any confirmed or suspected immunosuppressive or immunodeficient condition) or are confirmed to have an alteration of their initial immune status.

2080	
Vaccination done but: noncompliance with vaccination schedules (dates of vaccination not corresponding to protocol intervals or unknown vaccination dates)
 
Intervals between study visits for subjects vaccinated with Infanrix hexa at 2, 4 and 6 months of age is 42-104 days from birth to visit 1, 52-78 days from visit 1 to visit 2, 52-78 days from visit 2 to visit 3.
 
Intervals between study visits for subjects vaccinated with Infanrix hexa at 2, 3 and 4 months of age is 42-104 days from birth to visit 1, 21-48 days from visit 1 to visit 2, 21-48 days from visit 2 to visit 3.
 
Intervals between study visits for subjects vaccinated with Infanrix hexa at 2 and 4 months of age is 42 to 104 days from birth to visit 1, 52-78 days from visit 1 to visit 2.
 
Intervals between study visits for subjects vaccinated with Infanrix hexa at 3 and 5 months of age is 42 to 104 days from birth to visit 1, 52-78 days from visit 1 to visit 2.

2090	
Blood sample taken but: noncompliance with blood sampling schedules (dates of blood sampling not corresponding to adapted protocol intervals or unknown blood sample/vaccination dates) => 21-48 days from last vaccination visit to visit 4

2100	
Serological results not available for antigens POST vaccination (including lost samples, blood sample not done, unable to test, absence of parallelism) => no immunogenicity results available at visit 4.

2120	
Obvious incoherence, abnormal serology evolution or error in data (incoherence between CRF and results, wrong sample labelling)

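### Code 2100 makes the ATP analysis of Pre-Pri antibody persistence depend on having a Visit 4 result, so valid Visit 1 results are dropped (minor; secondary descriptive endpoint)

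*SAP*

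**What the plan says.** - **Endpoint.** SAP 4.2 lists "Persistence of antibodies before the first dose of" Infanrix hexa as a secondary endpoint, covering diphtheria, tetanus and the three pertussis antigens.
- **Analysis set.** SAP 6.3.1 bases the primary immunogenicity analysis on the ATP cohort and reports rates and GMCs "For each group, at each timepoint that a blood sample result is available". Templates 10 and 11 put Pre-Pri and Post-Pri rows on that one cohort.
- **What a code does.** SAP 5.2: "Elimination codes are used to identify subjects to be eliminated from analysis". No separate set is defined for Visit 1.
- **Code 2100.** SAP 5.2.3.1, under excluded subjects, applies it when there are "no immunogenicity results available at visit 4". Lost samples, samples not drawn and samples that cannot be tested all count.
- **Cohort definition.** On data availability, SAP 5.1.4 says: "This will include subjects for whom assay results are available for antibodies against at least one study vaccines antigen component". It names no timepoint. The same list also requires infants "who comply with the procedures and intervals defined in the protocol", and adds a 21–48 day window for "The interval between the last vaccination visit and post-primary blood sampling, considered for inclusion of a subject".
- **Back-up analysis.** SAP 6.3.1 adds a TVC analysis if more than 5% of enrolled infants in any group are excluded. SAP 5.1.2 sets no Visit 4 condition for it.
- **Subgroups.** SAP 6.3.2 specifies the subgroup tables for the ATP immunogenicity cohort only.

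**The concern.** The Pre-Pri sample is drawn before the first dose. A later dropout, a late second dose, a mistimed Visit 4 or a broken Visit 4 tube cannot change what it contains. Letting such events decide whether the Visit 1 result is analysed discards usable data and conditions a baseline quantity on later follow-up.

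The sample is this study's own measure of the maternal antibody present when priming starts, and the rationale (protocol 1.2.1) asks whether that antibody interferes with the response. The subgroup by gestational week at the maternal dose (SAP Section 10) bears directly on transferred antibody, and it has no alternative analysis set.

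**Working it through.** **1. Does the code act on the infant or on the visit?** Three places point to the infant: SAP 5.2 (codes identify subjects), the placement of 2100 under excluded subjects, and the shell of Template 5, where code 2100 is subtracted on the way to one ATP count:

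- dTpa: 300 − (23+3+1+6+3+20) = 300 − 56 = 244, as shown
- Control: 300 − (16+1+1+3+4+23) = 300 − 48 = 252, as shown

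The SAP says its templates were copied from recent studies, so these counts show structure only. They are not data from this trial.

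One place points the other way. When inheriting exclusions from study 116945, the SAP applies them all "except for the visit specific elimination codes (2090, 2100 and 2120"). It calls these codes visit specific but never says that they act by visit in this study.

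**2. Code against definition.** PT, FHA, PRN, D and T are vaccine antigens assayed at Visit 1 (protocol Table 12). An infant with only those results satisfies the data-availability bullet of SAP 5.1.4, yet code 2100 removes the infant. A missed Visit 4 can be read as failing the procedures-and-intervals bullet. A lost or untestable sample is not clearly covered by it. Codes 2080 and 2090 do implement that bullet, the 21–48 day window and the footnotes to protocol Tables 6–9.

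**3. Is the restriction needed?** No. SAP 6.3.1 already drops missing results measurement by measurement, so a Pre-Pri rate can be computed without a Visit 4 result.

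**4. When does the TVC analysis run?** The SAP 6.3.2 schedule table totals 601 infants. Assuming about 300 per group, 5% is 15, so 16 exclusions in one group trigger it. Protocol 10.3 expects a 10%–30% loss of evaluable subjects. If even the low end falls on enrolled infants, the trigger is met. Part of that loss may precede enrolment, since 601/680 = 88.4% of the maximum.

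**5. Precision.** The plan's own figures come first. With 340 per group, 340 × 0.9, 0.8 and 0.7 = 306, 272 and 238, against 300, 272 and 238 in protocol Table 22. At 95% of 300, Table 22 gives 91.9–97.2, and Clopper-Pearson for 285/300 reproduces it. The documents give no count of infants with a Pre-Pri result who would receive 2080, 2090 or 2100, so 5%–15% is an assumption: 601 × 0.05 to 601 × 0.15, or about 30 to 90 infants.

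| Assumed loss | n | Responders | Exact 95% CI | Width (points) |
|---|---|---|---|---|
| 0% | 300 | 285 | 91.9–97.2 | 5.3 |
| 5% | 285 | 271 | 91.9–97.3 | 5.4 |
| 15% | 255 | 242 | 91.4–97.3 | 5.8 |

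**6. Selection.** If a share m is removed and the Pre-Pri rate differs by d between removed and kept infants, the reported rate shifts by m × d. For assumed m of 2%–15% and d of 5–30 points, the shift runs from 0.02 × 5 = 0.1 to 0.15 × 30 = 4.5 points. At m = 7% and d = 10 it is 0.7. Nothing in the documents fixes m, d or the sign of d.

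**The case against.** The case on the other side is substantial, and several stronger inferences fail.

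- **A reader might infer that persistence is analysed only in followed-up infants.** That is not so for the main tables once exclusions pass 5% in a group. The TVC analysis then includes infants with only a Pre-Pri result, and if exclusions stay at or below 5% little is lost. What stands is that the TVC analysis is conditional and complementary, readmits infants excluded for reasons that matter at Visit 1 (preterm birth, for example), and has no subgroup version.
- **A reader might infer that the codes contradict the cohort's definition.** The bullets of SAP 5.1.4 are cumulative. Codes 2080 and 2090 follow them. Code 2100 is in tension with one bullet, most clearly for lost or untestable samples.
- **A reader might infer a biased result.** No mechanism in the documents ties Visit 1 antibody to a later missed visit or failed assay. Both groups receive the same infant vaccines, and protocol 5.3 keeps site staff blinded to the mother's allocation, so there is no evident driver of differential loss.
- **A reader might take transferred antibody to be the main question.** The primary objective is the response one month after the last dose, persistence is secondary, and cord-blood transfer belongs to study 116945.
- **One cohort is simpler.** It keeps broadly the same infants in adjacent Pre-Pri and Post-Pri rows. That is a real convenience, but no reason to discard valid results from a secondary endpoint.

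**Conclusion.** The point holds as a minor one. On the likelier, subject-level reading, code 2100 removes infants with valid Visit 1 results from the ATP persistence analysis because of events that cannot affect those results, and it is narrower than the data-availability bullet of SAP 5.1.4. Later-dose 2080 and 2090 do the same to Pre-Pri data while agreeing with the definition.

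The precision cost is about half a percentage point of interval width at the worst assumed loss of 15%. The size and direction of any bias cannot be derived. The gap matters most for the subgroup tables. SAP 6.3.2 names no timepoint for them, so this assumes that they carry Pre-Pri rows as the main templates do. All analyses are descriptive, so no test or decision rule is affected. The conclusion rests on the codes acting on subjects. If the visit-specific label was meant to govern this study too, the SAP needs only to say so for 2090 and 2100, and later-dose 2080 would remain.

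**What to change.** In SAP 5.2.3.1, state that codes 2090 and 2100 act by visit, and say which applies to 2120, which carries the same label. Reconcile 2100 with the data-availability bullet of SAP 5.1.4.

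Define a Pre-Pri evaluable ATP set that applies only exclusions settled by Visit 1: consent, eligibility, full-term birth, age at dose 1 (the birth-to-Visit-1 part of 2080), inherited maternal codes and a valid Pre-Pri result. Use it for the Pre-Pri persistence tables and their subgroups. Apply later-dose 2080, 2090 and 2100 only to Post-Pri and vaccine-response endpoints. Record the change in SAP Section 9, because protocol Tables 6–9 tie visit intervals to a single ATP immunogenicity cohort.

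The cost is one SAP paragraph and a second cohort flag, with no new data. N will differ between Pre-Pri and Post-Pri rows, which the templates already allow by showing N on each row. Making the TVC Pre-Pri table unconditional would be a lesser alternative: it removes the 5% condition but leaves the subgroup tables as they are.
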